Each child and their caregiver(s) will participate in one appointment. After consent, they will be randomly assigned to one of two telemedicine procedures (TELE-STAT or TELE-ASD-PEDS). The child and parent will be led through the screening tool by a remote psychologist (approximately 30 to 45 minutes). The telemedicine procedure, regardless of which one the family is assigned to) involves behavioral interactions that are coded by the examiner on paper forms. Parents will be in the same room as their child at all times and will also be asked to interact with their child in specific ways in order to elicit social, communication, and play skills in their child.

Aim 2:

Each child and their caregiver(s) will participate in one appointment. The appointment will include 2 parts: 1. telemedicine tool and 2. gold standard diagnostic evaluation. After consent and being randomly assigned to one of two telemedicine procedures, the child and parent will be led through the screening tool by a remote psychologist (approximately 45 minutes to 1 hour). Following the telemedicine procedure, the child will receive a gold standard diagnostic evaluation (2 to 3 hours) in person by a licensed clinician.

Behavioral Observation will be conducted in both the telemedicine and gold standard evaluations. This will be done as part of the TELE-STAT (telemedicine autism screener), TELE-ASD-PEDS (telemedicine autism screener), and ADOS-2 (gold standard autism test). Both the telemedicine screeners and the ADOS-2 procedures involve behavioral interactions that are coded by the examiner on paper forms. Parents will be in the same room as their children at all times and will also be asked to interact with their child in specific ways in order to elicit social, communication, and play skills in their child.

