The clinician conducting the telemedicine procedure will be blind to the participant's existing diagnosis (autism or other developmental delay). Parents will be asked not to divulge this information in order to maintain research integrity.

Aim 2:

The clinician conducting the telemedicine procedure does not need to be blind because all participants will have necessarily not been evaluated before. The clinician who completes the gold standard diagnostic evaluation, however, will be blinded to the diagnostic impression and certainty of the clinician who conducted the telemedicine procedure. Parents will also be blinded to the results of the telemedicine procedure. They will not be blinded to any study procedures, the purpose of the study, or the results of the gold standard evaluation, which will include diagnostic feedback and recommendations.

This study does not involve deception.

6

Procedures:

Please indicate all procedures and activities performed for research purposes only and the frequency at which they occur in the study (e.g., skin biopsy, 3 times).

Procedure/Activity	Frequency
TELE-STAT (occurs in Aim 1 and Aim 2)	1 time, approximately 30 minutes
TELE-ASD-PEDS (occurs in Aim 1 and Aim 2)	1 time, approximately 30 minutes
Diagnostic Certainty Form	Approximately 5 minutes
Comprehensive interview with parents (occurs only in Aim 1)	1 time, 30 to 45 minutes
VABS-3 (occurs only in Aim 1)	1 time, 30 minutes
MSEL (occurs only in Aim 1)	1 time, 30 minutes
ADOS-2 (occurs only in Aim 1)	1 time, 30 to 45 minutes
Medical History/Background Information (occurs only in Aim 1)	1 time, 15 minutes
Parent Feedback Form (occurs in Aim 1 and 2)	1 time, 10 minutes
ALFA-Q (completed by clinicians and parents, both in Aim 1 and Aim 2)	

Data and Safety**Aim 1:**

Participants will be recruited from families who have come through our diagnostic clinics whose children have been diagnosed with autism or other developmental delays and who have previously signed consent to be contacted for research.

Aim 2:

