necessary for honing the procedures utilized in our rigorous evaluation of measure use in Aim 2. Although we are examining diagnostic agreements in this study, the larger rigorous, blinded evaluation described in Aim 2 is ultimately necessary to adequately test and understand the potential added value of these tools.

Specific Aim 2: After optimizing use and administration characteristics, we will deploy the refined TELE-STAT (n=60) and TELE-ASD-PEDS (n=60) assessment tools with clinically referred, undiagnosed children and rigorously evaluate their ability to facilitate accurate telemedicine supported diagnostic decision making. Secondary analyses will also compare the characteristics of these tools across these independent samples as well as potential scoring thresholds for the instruments for subsequent evaluation. Our team of 10 clinical providers will be asked to complete 6 remote evaluations utilizing TELE-STAT and 6 remote evaluations with TELE-ASD-PEDS. At the end of the procedure, the psychologist will complete ratings of clinical best estimate (CBE) diagnosis and diagnostic certainty (Yes / No ASD; Yes / No / Uncertain classification, as well as Likert rating of certainty ranging from 1= 'uncertain' to 5 = 'very certain'). Families will then immediately participate in a blinded in-person comprehensive assessment conducted by a different licensed psychologist. This assessment will include administration of a measures of cognitive functioning (MSEL), adaptive behavior (VABS-3), autism symptoms (ADOS-2), as well as clinical interviewing surrounding medical, behavioral, and developmental history. The blinded provider will then independently assign diagnostic and certainty ratings, and provide clinical information to the family.

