The sample size of 60 per instrument is deemed adequate for initial preliminary evaluation of performance characteristics. Given the diagnostic confirmation rates of the referral base for this study (roughly 2/3 ASD; 1/3 non-ASD), we will have data capable of describing the concurrent validity and agreement of remote diagnostic decision making and telemedicine tool use with clinical best estimate diagnosis using a traditional assessment battery. We will examine agreements (True/False Positives and Negatives) and corresponding sensitivity, specificity, as well as positive and negative predictive value related to both ASD and non-ASD classifications. Based on our preliminary data, we hypothesize that clinicians utilizing both of the telemedicine assessment procedures will be able to accurately identify: (a) $\geq 60\%$ of children with ASD with certainty (b) $\geq 50\%$ children without ASD with certainty, and (c) $\leq 10\%$ of children will be misclassified with ASD with certainty. Certainty is operationalized as the clinician forced choice and Likert rating of certainty in classification (i.e. clinician when given option of uncertainty/other chooses ASD with high certainty). We will also utilize non-parametric comparisons (chi-square) to evaluate differential performance clinical diagnosis using these tools relative to one another and ADOS-2 classification scores. We will not be adequately powered to systematically examine variability related to certain child, family, and clinician related characteristics; however, we will have preliminary data that could be examined to foster future systematic exploration of these factors in a larger controlled study, if successful. In similar form, our sample size with each instrument will afford us the ability to preliminarily apply signal detection to potential cutoff scores from the adapted rating (TELE-ASD-PEDS) and scoring procedures (TELE-STAT) associated with these instruments.

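### The ADOS-2 helps form the Aim 2 reference diagnosis, so contrasting its performance with that of telemedicine diagnosis is expected to favour the ADOS-2 and cannot be cleanly interpreted

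*Combined protocol and SAP*

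**What the plan says.** Four statements bear on this point.

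- **Comparison.** Statistical Design and Power, Specific Aim 2, plans chi-square tests to "evaluate differential performance clinical diagnosis using these tools relative to one another and ADOS-2 classification scores".
- **Reference.** The same section says that the data will describe "agreement of remote diagnostic decision making and telemedicine tool use with clinical best estimate diagnosis using a traditional assessment battery". Sensitivity, specificity and predictive values follow from that comparison. No other reference diagnosis is defined.
- **What goes into the reference.** The in-person battery is set out in the same section: "This assessment will include administration of a measures of cognitive functioning (MSEL), adaptive behavior (VABS-3), autism symptoms (ADOS-2), as well as clinical interviewing". The next step is: "The blinded provider will then independently assign diagnostic and certainty ratings".
- **Blinding.** Under Blinding, Aim 2, the in-person clinician "will be blinded to the diagnostic impression and certainty of the clinician who conducted the telemedicine procedure". Nothing masks that clinician to the ADOS-2, which Behavioral Observations, Aim 2, lists as "ADOS-2 (gold standard autism test".

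The plan does not mention that the ADOS-2 is both a comparator and a component of the reference.

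**The concern.** When one of two measures being compared helps to decide who counts as having ASD, its agreement with that decision is raised by construction. This is incorporation bias. Here it acts on one side only: the ADOS-2 informs the reference, and the telemedicine rating is deliberately kept out of it. The blinding is right for estimating telemedicine accuracy, but it makes the two measures unequal when they are set against each other.

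Two misreadings are possible, one for each meaning of the sentence. If accuracies are contrasted, a telemedicine diagnosis as accurate as the ADOS-2 may appear worse. If only agreement with the ADOS-2 is tabulated, good agreement with both it and the clinical best estimate may be taken as two validations, although the second standard partly contains the first.

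The choice of test does not settle this. Telemedicine diagnosis and ADOS-2 are measured on the same children, so an ordinary chi-square also ignores the pairing. That is a separate matter: a correctly paired test would have the same bias.

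**Working it through.** **No plan figure to reproduce.** The documents give no accuracy for the ADOS-2, no expected difference and no power calculation for this comparison. The structural point comes from the text; the arithmetic below only shows its possible size.

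**Inputs, all assumed.** ADOS-2 and telemedicine are each correct in 0.85 of children, and the provider's other information in 0.90. Errors are independent. Where the ADOS-2 and the other information conflict, the provider follows the ADOS-2 in a share *w* of children. Accuracy is taken as equal in ASD and non-ASD children, so prevalence drops out of overall agreement.

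**Steps.**

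1. ADOS-2 and other information coincide: 0.85 × 0.90 + 0.15 × 0.10 = 0.765 + 0.015 = 0.78. They conflict in 0.22.
2. ADOS-2 agreement with the reference: 0.78 + 0.22*w*.
3. Accuracy of the reference: 0.765 + (1 − *w*) × 0.15 × 0.90 + *w* × 0.85 × 0.10 = 0.900 − 0.050*w*.
4. Telemedicine agreement with the reference: 0.85 × acc + 0.15 × (1 − acc) = 0.15 + 0.70 × acc = 0.780 − 0.035*w*.
5. Gap: (0.78 + 0.22*w*) − (0.78 − 0.035*w*) = 0.255*w*.

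| *w* | Reference accuracy | ADOS-2 agreement | Telemedicine agreement | Gap |
|---|---|---|---|---|
| 0 | 0.900 | 0.780 | 0.780 | 0 |
| 0.25 | 0.8875 | 0.835 | 0.77125 | 0.06375 |
| 0.50 | 0.875 | 0.890 | 0.7625 | 0.1275 |
| 1 | 0.850 | 1.000 | 0.745 | 0.255 |

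The first row is the control: with no incorporation, two equally accurate measures look equal.

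**Other accuracies.** Here the plan's ASD share of 2/3 is used, and both measures again have the same true sensitivity and specificity. At 0.90/0.80, ADOS-2 against telemedicine agreement is 0.845 against 0.788 (*w* = 0.25) and 0.897 against 0.783 (*w* = 0.5). At 0.80/0.70 it is 0.785 against 0.697 and 0.857 against 0.680. The direction is the same; the size varies.

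**Shared errors.** A simulation dropped the independence assumption. Each measure is a noisy score, true accuracy is about 0.84 for both, the ASD share is 2/3, and the reference is a weighted sum of the ADOS-2 score and the other in-person judgement. (This weight applies to scores and is not *w*.) Cells show ADOS-2 / telemedicine agreement with the reference.

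| Correlation of telemedicine error with the other in-person judgement | ADOS-2 weight 0.3 | 0.5 | 0.7 |
|---|---|---|---|
| 0 | 0.818 / 0.777 | 0.867 / 0.787 | 0.916 / 0.777 |
| 0.3 | 0.817 / 0.803 | 0.866 / 0.805 | 0.915 / 0.787 |
| 0.6 | 0.817 / 0.840 | 0.867 / 0.827 | 0.916 / 0.799 |

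At weight 0.3 and correlation 0.6 the gap reverses. Adding a 0.3 correlation between telemedicine and ADOS-2 errors narrows it further: a near tie at weight 0.3 and correlation 0.3 (0.818 / 0.817), and a larger reversal at weight 0.3 and correlation 0.6 (0.818 / 0.860). At weights 0.5 and 0.7 the gap stayed against telemedicine in every setting, though it fell to 0.867 / 0.856 in the closest.

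**Agreement-only reading.** In the first model, telemedicine agrees with the ADOS-2 in 0.85 × 0.85 + 0.15 × 0.15 = 0.745 of children whatever *w* is, so incorporation does not distort that figure. It is still not independent of the comparison with the reference: the ADOS-2 and the reference coincide in 0.78 + 0.22*w* of children, and at *w* = 1 the two agreement figures are the same number.

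**The case against.** The strongest reply is that the sentence is ambiguous and the affected analysis is small. The wording can mean that telemedicine diagnosis is simply tabulated against ADOS-2 classification as a second criterion, and the gold-standard label given to the ADOS-2 fits that. The plan nowhere says that ADOS-2 sensitivity or specificity against the clinical best estimate will be calculated. On that reading the gap does not arise. This stands, and it is why the conclusion is conditional. Still, a test of differential performance relative to the ADOS-2 reads more naturally as a contrast, and the agreement reading leaves the problem of counting one validation twice.

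It is also fair that independent errors are unlikely: both evaluations are of the same child at one appointment, by psychologists looking at overlapping behaviour. The direction is therefore expected, not certain.

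A reader might infer that equally accurate telemedicine must look worse, by up to 25 points. The documents do not support this. That figure needs a provider who always lets the ADOS-2 override everything else, which fits poorly with a battery that also has cognitive and adaptive measures and an interview. The plan gives no weight for the ADOS-2.

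The Procedures table lists the ADOS-2, MSEL and VABS-3 under Aim 1 only, against Behavioral Observations and Specific Aim 2. These passages must be reconciled. The table does not rescue the comparison, which needs the ADOS-2 in Aim 2. Using the ADOS-2 to reach a best-estimate diagnosis is not itself criticised.

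**Conclusion.** The concern holds in conditional form. If ADOS-2 and telemedicine accuracy against the clinical best estimate are contrasted, the ADOS-2 is expected to have an advantage that comes from the design rather than from better accuracy. Under the main assumptions this is about 6 to 13 points for *w* between 0.25 and 0.5. The weight and every accuracy value are assumed, and shared errors could shrink or reverse the gap. Because the plan will not know the weight, an observed difference in either direction could not be attributed to accuracy.

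A reader might also infer that the Aim 2 accuracy results are compromised, or that the plan intends to claim superiority, inferiority or a second validation. Neither follows. Sensitivity, specificity and predictive values of telemedicine diagnosis use a reference blinded to it. The 60%, 50% and 10% benchmarks do not use the ADOS-2 as comparator. Neither TELE-STAT nor TELE-ASD-PEDS enters the reference, so their comparison with each other is untouched. The plan states no such claim about the ADOS-2; the point is to rule it out before results are read. This is a cheap and worthwhile correction to a secondary analysis.

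**What to change.** In Statistical Design and Power, Specific Aim 2:

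1. Remove the ADOS-2 from the differential-performance test, and confine that test to TELE-STAT against TELE-ASD-PEDS.
2. State that the accuracy of telemedicine diagnosis and tool scores is judged only against the blinded provider's clinical best estimate.
3. Report telemedicine diagnosis against ADOS-2 classification as descriptive agreement, without a test.
4. Add that the ADOS-2 contributes to the clinical best estimate, so no superiority, inferiority or second-validation claim will be drawn from that agreement.

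The cost is analysis wording only, with no new data, visits or participants. The downside is giving up a performance claim relative to the ADOS-2, which this design cannot support. If the sponsor wants to keep that claim, the reference for this one comparison would have to be assigned by a rater masked to both the ADOS-2 and the telemedicine result, which adds rater time.
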